Section 9.2.5. Evaluation of humoral immune response at Month 25 (secondary objective)		
Section 9.2.6. Evaluation of cellular immune response at Month 25 (secondary objective)	These sections were updated where applicable following the implementation of a representation with an additional	Results from previous studies using the
Section 9.2.7. Evaluation of reactogenicity and safety profile following revaccination in the RSV_annual and RSV_flexible revaccination groups	of a revaccination with an additional dose of the RSVPreF3 OA investigational vaccine at Month 24 for participants from the RSV_flexible revaccination group.	same study intervention showed that participants from this group might benefit from an additional dose at that timepoint.
Section 9.4.1. General considerations		
Section 9.5.1.1. Analyses for objectives and endpoints		

212496 (RSV OA=ADJ-004) Protocol Amendment 1 Final

Section # and title	Description of change	Brief rationale		
Section 9.3. Population for analyses				
Section 9.4.1.2. Immunogenicity				
Section 9.4.2. Demographics and participants' disposition		Following the addition of a revaccination at		
Section 9.4.3.1. Humoral immune response – up to Month 12	Analyses were updated.	Month 24 for the RSV_flexible revaccination group, and to align with other Phase 3 RSV OA studies, some immunogenicity and safety analyses were		
Section 9.4.4.1. Humoral immune response		updated/clarified.		
Section 9.4.4.2. Cell- mediated immune response				
Section 9.4.4.3. Safety analysis				
Section 10.3.5.1. Potential immune-mediated diseases	The list of pIMDs has been revised.	The list has been updated following a regular safety review and to include possible immune-mediated adverse events of special interest.		
Section 10.4.2. Requirements for Germany	Remote Source Data Verification (rSDV) during exceptional situations in Germany was added.	Instructions with regards to remote monitoring were added to allow this study procedure to be performed even in case of exceptional circumstances (e.g., in case of a lockdown).		

212496 (RSV OA=ADJ-004) Protocol Amendment 1 Final

TABLE OF CONTENTS

				PAGE	
SP	ONSO	R INFORI	MATION	6	
PR			NDMENT SUMMARY OF CHANGES TABLE		
	Docui	ment histo	ory	7	
	List o	f main cha	anges in the protocol and their rationale:	7	
1.	PROI	rocol s	UMMARY	18	
••	1.1.		is		
	1.2.		a		
	1.3.		lle of Activities (Amended: 01 April 2022)		
2.	INITO	ODLICTIC	ON	20	
۷.					
	2.1. 2.2.		Rationale		

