- **Study visits should preferably be done on site. As of Protocol Amendment 1 implementation, if deemed necessary, local regulations allow, and quality of study procedures is maintained, study visits during the follow-up phases can be done at home or at the LTCF, as per local regulation. Home visits are not allowed for the CMI subset (due to sensitivity of CMI samples), except in special circumstances and with the approval of the GSK Central study team. For participants without blood sample collections (i.e., for participants only being followed up for safety), contact should be attempted only if site visit is not possible at Months 6, 18, 30 and 36. For contacts, multiple formats can be proposed by the study site. These contacts may be done via email, text message, or phone call for example. The most appropriate format should be agreed between site staff and the study participant. Messaging services and email may be used as a screening to check if the participant has anything to report. If the participant answers "Yes" for at least one of the items of interest, then a phone call must be done to get the details on the event(s). Receipt of the message must be confirmed by the participant or caregiver, as applicable.
- ¹ Freely given and written informed consent must be obtained from each study participant prior to participation in the study. The participant's informed consent may be obtained prior to Visit 1.
- ² Any vaccination administered up to 1 year before administration of the first dose of study vaccine should be recorded in the eCRF. Administration of *Shingrix* at any timepoint (even if longer than 1 year before the first study dose) should be recorded in the eCRF.
- ³ Blood samples for humoral immunity (HI) and for CMI will be taken from the same ~345 participants. The remaining ~645 participants will have no blood draws. Refer to Section 6.3.4 for details.
- ⁴ Recording of any SAE or any pIMD should only be done in the 6-month post-vaccination period, i.e., from Day 1 to Month 6, from Month 12 to Month 18, and from Month 24 to Month 30.
- ⁵ SAEs related to study participation, or to a concurrent GSK medication/vaccine should be collected from the time of consent obtained (prior to administration of Dose 1) up to study end.
- 6 Blood sampling should be performed prior to vaccination (this has been clarified for the vaccination visit occurring after implementation of Protocol Amendment 1).

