10.3.5. Adverse events of special interest

10.3.5.1. Potential immune-mediated diseases

pIMDs are a subset of AEs of special interest that include autoimmune diseases and other inflammatory and/or neurologic disorders of interest which may or may not have an autoimmune etiology. AEs that need to be recorded and reported as pIMDs include those listed in the Table 27 (please refer to the Section 10.3.8.1 for reporting details).

However, the investigator will exercise his/her medical and scientific judgment to determine whether other diseases have an autoimmune origin (i.e. pathophysiology involving systemic or organ-specific pathogenic autoantibodies) and should also be recorded as a pIMD.

Table 27 List of potential immune-mediated diseases (pIMDs) (Amended: 01 April 2022)

Medical Concept	Additional Notes		
Blood disorders and coagulopathies			
Antiphospholipid syndrome			
Autoimmune aplastic anemia			
Autoimmune hemolytic anemia	Includes warm antibody hemolytic anemia and cold antibody hemolytic anemia		
Autoimmune lymphoproliferative syndrome (ALPS)			
Autoimmune neutropenia			
Autoimmune pancytopenia			
Autoimmune thrombocytopenia	Frequently used related terms include: "autoimmune thrombocytopenic purpura", "idiopathic thrombocytopenic purpura (ITP)", "idiopathic immune thrombocytopenia", "primary immune thrombocytopenia".		
Evans syndrome			
Pernicious anemia			
Thrombosis with thrombocytopenia syndrome (TTS)			
Thrombotic thrombocytopenic purpura	Also known as "Moschcowitz-syndrome" or "microangiopathic hemolytic anemia"		
Cardio-pulmonary inflammatory disorders			
	Including but not limited to:		
Idionathia Myagarditia/Pariaarditia	Autoimmune / Immune-mediated myocarditis		
Idiopathic Myocarditis/Pericarditis	Autoimmune / Immune-mediated pericarditis		
	Giant cell myocarditis		
	Including but not limited to:		
Idiopathic pulmonary fibrosis	 Idiopathic interstitial pneumonia (frequently used related terms include "Interstitial lung disease", "Pulmonary fibrosis", "Immune-mediated pneumonitis") 		
	Pleuroparenchymal fibroelastosis (PPFE)		
Pulmonary alveolar proteinosis (PAP)	Frequently used related terms include: "pulmonary alveolar lipoproteinosis", "phospholipidosis"		

212496 (RSV OA=ADJ-004) Protocol Amendment 1 Final

Medical Concept	Additional Notes		
Endocrine disorders			
Addison's disease			

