- The number and percentage of participants with at least one report of SAE classified by the MedDRA Primary SOC, HLT and PTs and reported from Dose 1 up to 6 months post-Dose 1 and from revaccination dose up to 6 months post-revaccination will be tabulated with exact 95% CI. The same tabulation will be presented for causally related SAEs and fatal SAEs,.
- The number and percentage of participants with at least one report of causally related SAEs classified by the MedDRA Primary SOC, HLT and PTs will be reported after each dose and from Day 1 up to study end with exact 95% CI. The same tabulation will be presented for fatal SAEs.
- All SAEs will also be described in detail in a tabular listing.
- All AEs/SAEs leading to study/intervention discontinuation from dose 1 up to study end will be tabulated.
- The number and percentage of participants with at least one report of pIMD classified by the MedDRA Primary SOC, HLT and PTs and reported from Dose 1 up to 6 months post-Dose 1 and from revaccination dose up to 6 months post-revaccination will be tabulated with exact 95% CI. The same tabulation will be presented for causally related pIMDs
- The number and percentage of participants with at least one causally related pIMD classified by the MedDRA Primary SOC, HLT and PTs will be reported after each dose and from Day 1 up to study end with exact 95% CI.
- All pIMDs will also be described in detail in a tabular listing.
- The analyses of unsolicited AEs will include SAEs (unless otherwise specified).

The analysis of safety will also be performed by age category (age at Dose $1: \ge 65$ YOA, ≥ 70 YOA, ≥ 80 YOA, 60-69 YOA and 70-79 YOA) and region (North America, Europe, Asia).

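### The pIMD list was widened on net between most Dose 1 windows and all Month 24 windows, yet the SAP tabulates pIMDs dose by dose without a common list

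*SAP*

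**What the plan says.** Protocol Table 6 makes the occurrence of pIMDs up to 6 months after each vaccination a secondary endpoint, and Section 2.3.1 names pIMDs as the potential risk of the adjuvant system. Section 10.3.5.1 ties recording to a list: "AEs that need to be recorded and reported as pIMDs include those listed in the Table 27". It also asks investigators to "determine whether other diseases have an autoimmune origin" and to record those as pIMDs too.

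The protocol's list of main changes for Amendment 1 says "The list of pIMDs has been revised", and gives the reason: "The list has been updated following a regular safety review and to include possible immune-mediated adverse events of special interest". Current Table 27 carries the date 01 April 2022.

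SAP Amendment 3, Section 5.4.4, counts those having "at least one report of pIMD classified by the MedDRA Primary SOC, HLT and PTs and reported from Dose 1", over a 6-month window, and does the same over 6 months from each revaccination. It also reports related pIMDs after each dose and to study end, and lists every pIMD. Section 5.4.5 adds pIMDs within 30 days of each vaccination. Neither section names a list version or a common definition. Section 8, which records departures from the protocol's analysis, adds per-dose pIMD outputs but does not mention the list. SAP Amendments 2 (20 June 2022) and 3 (27 March 2023) both postdate the new list.

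On collection, Protocol 10.3.8.1 records all unsolicited AEs for 30 days after each dose, and SAEs and pIMDs for 6 months. In RSV_1dose, pIMDs regardless of causality are recorded only to Month 6 (Table 3, footnote 5).

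**The concern.** Updating a safety list during a trial is not a fault, and a difference between old and new protocol text is not the issue. The issue is that the case definition of a per-dose endpoint changed while that endpoint was being collected, and the tables set the doses beside one another as if it had not.

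The comparison at stake is the one a reader will look for first: are there more pIMDs after a second or third adjuvanted dose than after the first? If Dose 1 is counted largely under one list and Month 24 under a wider one, the two percentages can differ with no change in risk. No concurrent group separates the effects, because RSV_1dose has no all-pIMD recording after Month 6.

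**Working it through.** **1. The plan's own safety figure.** Table 23 uses 1 − (1 − p)^n. With p = 0.5%, n = 990 gives 99.3% and n = 330 gives 80.9%, as stated. This sizing concerns a generic AE. The documents give no pIMD rate.

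**2. What changed in the list.** I compared Table 27 with the list it replaced, shown in Protocol Section 10.6. Seventeen current rows have no counterpart: autoimmune lymphoproliferative syndrome, Evans syndrome, TTS, thrombotic thrombocytopenic purpura, pulmonary alveolar proteinosis, autoimmune testis/ovary disease, autoimmune hyperlipidemia, insulin autoimmune syndrome, erythema multiforme, reactive granulomatous dermatitis, pyoderma gangrenosum, capillary leak syndrome, immune-mediated enhancement of disease, IgG4-related disease, Langerhans' cell histiocytosis, overlap syndrome and Susac's syndrome. Others were extended (myocarditis now includes pericarditis; Kawasaki's disease became multisystem inflammatory syndromes). At least one named item is gone: polyneuropathies associated with monoclonal gammopathy. The net change is a widening.

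**3. Timing.** Month 12 doses are allowed at 350–380 days and Month 24 doses at 715–745 days after Dose 1. Protocol 9.4 requires the SAP to be final before the first visit, and the first SAP is dated 9 February 2021.

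- Earliest Month 24 dose: 9 February 2021 + 715 days = 25 January 2023, which is 299 days after 01 April 2022. Counting instead from the original protocol date, 28 October 2020 + 715 days = 13 October 2022, still later. The RSV_flexible Month 24 dose exists only under Amendment 1.
- Earliest Month 12 dose: 9 February 2021 + 350 days = 25 January 2022. Its 180-day window ends no earlier than 24 July 2022, so no Month 12 to 18 window had closed when the list was issued.
- A 180-day Dose 1 window closed before 01 April 2022 if Dose 1 was given by about 3 October 2021. Enrolment dates are not given. Footnote 6 to Table 1, attached to Month 24, reads "Blood sampling should be performed prior to vaccination (this has been clarified for the vaccination visit occurring after implementation of Protocol Amendment 1". It concerns blood sampling, but it treats Month 24 as the vaccination visit that follows the amendment.

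01 April 2022 is the issue date. Sites changed over after ethics approval, on dates not given.

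**4. Which events are affected.**

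| Event | Days 1–30 after a dose | After day 30 to 6 months |
|---|---|---|
| Newly listed, serious | Recorded; pIMD label depends on list | Recorded; pIMD label depends on list |
| Newly listed, non-serious | Recorded as unsolicited AE; pIMD label depends on list | Recording largely depends on list |

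Classification is affected throughout. Collection is affected only for non-serious events after day 30, apart from those leading to withdrawal.

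**5. Illustration only.** Let p be the 6-month risk under the old list and f the factor by which the new list raises capture, with true risk unchanged. Then f = (old + new)/old. Assuming old 0.3–0.5% and new 0.1–0.3%, f runs from (0.5 + 0.1)/0.5 = 1.2 to (0.3 + 0.3)/0.3 = 2.0. If the added concepts contribute nothing, f = 1.0. The chance that the Month 24 percentage exceeds the Dose 1 percentage, treating the windows as independent binomials with p = 0.5%, is:

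| Group, N at Dose 1 v Month 24 | f | Expected cases | Chance of rise | With one list |
|---|---|---|---|---|
| RSV_annual, 990 v 990 | 1.25 | 5.0 v 6.2 | 58.7% | 43.6% |
| RSV_annual, 990 v 990 | 2.0 | 5.0 v 9.9 | 88.0% | 43.6% |
| RSV_annual, 990 v 634 | 1.25 | 5.0 v 4.0 | 62.3% | 49.7% |
| RSV_flexible, 330 v 330 | 1.25 | 1.7 v 2.1 | 47.6% | 38.5% |

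The 634 is 990 × 0.8 × 0.8, borrowing the protocol's 20% yearly non-evaluable rate as assumed attrition. Expected counts then fall while the percentage still tends to rise. At f = 1.0 the last two columns coincide.

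**The case against.** Much of the case on the other side stands.

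- **A rise can be traced.** Tables by SOC, HLT and PT and a full pIMD listing, with only a handful of cases per window on the rates assumed above, let a reader see whether it comes from newly listed terms. One might infer that a list artefact could not be told apart from a true effect of repeated dosing; the planned outputs do not support that. What they do not repair is the headline percentage and its confidence interval, or events never recorded.
- **The collection gap is narrow.** Some additions, such as TTS or capillary leak syndrome, would often meet the SAE definition and be recorded anyway. The 30-day table has a classification problem only.
- **Investigators could already report unlisted diseases of autoimmune origin.** The amendment history for 10.3.5.1 shows only the table changing, so that clause appears to predate the amendment. It depends on judgement and does not clearly reach additions that are not autoimmune.
- **Some changes elaborate old headings.** Interstitial pneumonia and thyrotoxicosis terms are examples. The count of 17 leaves these out.
- **The bias is not strictly one-way.** One item was dropped, and Protocol 7.1.2 withholds further doses after certain new or worsened pIMDs or related SAEs, which works against a rise.
- **All analyses are descriptive.** No test is distorted. A descriptive per-dose table still invites comparison across its columns.

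**Conclusion.** The point holds as one of comparability. Under the SAP as written, the per-dose percentages with at least one pIMD rest on different lists: mostly the old one after Dose 1, probably both after Month 12 in RSV_annual, and the new one after Month 24. Some of any apparent rise after revaccination may reflect the list. The net direction is probably upward.

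The size cannot be derived from the documents. The factor of 1.2 to 2.0 is arithmetic on assumed rates, not an estimate. Its upper end needs the added concepts to be as frequent together as everything on the old list, which already held gout, psoriasis, polymyalgia rheumatica and rheumatoid arthritis. A factor near 1.0 is equally compatible with the documents.

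A reader might go further and conclude that any rise after revaccination is an artefact, or that the pIMD results are invalid. The documents support neither. Between-group comparisons within the same vaccination window, such as the third dose in RSV_annual against the second in RSV_flexible at Month 24, share a list and are not affected in this way. The Dose 1 and Month 12 timing is partly inferred, since enrolment and site implementation dates are absent.

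**What to change.** Keep the planned pIMD tables on the full current list, and amend SAP 5.4.4 and 5.4.5 as follows:

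1. Add a supplementary dose-by-dose pIMD table, for the 6-month and 30-day windows, restricted to concepts on both the original and the Amendment 1 lists.
2. Flag newly listed concepts in the full tables and the listing, showing onset relative to implementation of Amendment 1 at the site.
3. Footnote that newly listed non-serious events after day 30 were not systematically collected under the old list.
4. Make any check of already recorded AEs and SAEs against the new list an analysis-level MedDRA term flag. Reclassification by sites could trigger causality review and expedited reports under Protocol 8.3.3, and is not needed for this purpose.

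The cost is a mapping from medical concepts to MedDRA terms and one extra set of tables, with no new data. The mapping needs some medical judgement, because many rows are open-ended. The common-list table omits the newly listed conditions, which is why the full table should stay beside it.

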5.4.5. Additional considerations

- Compliance in completing solicited events information will be tabulated after each dose .
- The number and percentage of participants with at least one administration site event (solicited only), with at least one systemic event (solicited only) and with any solicited event during the 4-day follow-up period after each dose will be tabulated with exact 95% CI. The same computations will be done for Grade 3 AEs and for AEs resulting in a medically attended visit.
- The number of days with solicited events reported during the 4-day follow-up period will be tabulated for each solicited event, after each dose using descriptive statistics (mean, min, Q1, median, Q3, maximum).
- The number of each solicited events (any and Grade 3) that are ongoing beyond the 4-day follow-up period will be reported with the duration in days (mean, min, Q1, median, Q3, maximum).
- The list of solicited administration site and systemic events, and definition of intensity are described in Section 10.3.3 and 10.3.9.1 of the protocol.
- The number and percentage of participants with at least one report of SAE classified by the MedDRA Primary SOC, HLT and PTs and reported within 30 days following each vaccination will be tabulated with the exact 95% CI. The same tabulation will be presented for pIMDs.

The measurement of erythema/swelling (in mm) and fever (in °C/F) will be categorized as follows:

Grading	Erythema/swelling	Fever
0:	≤ 20 mm	< 38.0°C (100.4°F)
1:	> 20 - ≤ 50 mm	≥ 38.0°C(100.4°F) - ≤ 38.5°C(101.3°F)
2:	> 50 - ≤ 100 mm	> 38.5°C(101.3°F) - ≤ 39.0°C(102.2°F)
3:	> 100 mm	> 39.0°C(102.2°F)

Table 7Intensity grading scale for solicited events

Combined Solicited events and Unsolicited AEs

For clinicaltrials.gov and EudraCT posting purposes, a summary of combined solicited and unsolicited non-serious adverse events will be produced by System Organ Class and preferred terms and according to occurrence of each event.

Solicited events will be coded by MedDRA as per the following codes:

Solicited event	Lower level term code	Corresponding Lower level term decode
Pain	10022086	Injection site pain
Erythema	10022061	Injection site erythema
Swelling	10053425	Injection site swelling
Fever	10016558	Fever
Headache	10019211	Headache
Fatigue	10016256	Fatigue
Myalgia	10028411	Myalgia
Arthralgia	10003239	Arthralgia

5.4.5.1. Concomitant Medication

Medications will be coded using the GSKDRUG dictionary.

5.4.6. Sensitivity Analyses

If more than 10% of participants miss the revaccination dose or don't have safety data reported after revaccination, the safety analysis described in section 5.4.4 will also be conducted on participants with full follow-up (attending all study visits).

The goal of this sensitivity analysis is to determine the extent to which results might be impacted by considering the different scenarios.

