- **Study visits should preferably be done on site. **As of Protocol Amendment 1 implementation,** if deemed necessary, **local regulations allow, and quality of study procedures is maintained,** study visits during the follow-up phases for the humoral subset can be done at home or at the LTCF, as per local regulation. **Home visits are not allowed for the CMI subset** (due to sensitivity of CMI samples) except in special circumstances and with the approval of the GSK Central study team.
- ¹ Freely given and written informed consent must be obtained from each study participant prior to participation in the study. The participant's informed consent may be obtained prior to Visit 1.
- ² Any vaccination administered up to 1 year before administration of the first dose of study vaccine should be recorded in the eCRF. Administration of *Shingrix* at any timepoint (even if longer than 1 year before the first study dose) should be recorded in the eCRF.
- ³ Blood samples for humoral immunity will be taken from all participants. Refer to Section 6.3.4 for details.
- ⁴ CMI blood samples should only be taken from ~115 participants. Refer to Section 6.3.4 for details.
- ⁵ Recording of any SAE or any pIMD should only be done in the 6-month post-vaccination period, i.e., from Day 1 to Month 6 and from Month 24 to Month 30.
- ⁶ SAEs related to study participation, or to a concurrent GSK medication/vaccine should be collected from the time of consent obtained (prior to administration of Dose 1) up to study end.
- ⁷ Blood sampling should be performed prior to vaccination (this has been clarified for the revaccination visit occurring after implementation of Protocol Amendment 1).
- ⁸ Visits at Month 30 must not be performed before the 6-month post-vaccination timepoint to allow collection of safety data up to at least 6 months after each vaccination for each participant (this has been clarified for the revaccination visit occurring after implementation of Protocol Amendment 1).

^{*}Refer to Table 7 for the description of study groups.

Table 3 Schedule of activities: RSV_1dose* (Amended: 01 April 2022)

Type (V = visit)**	٧	V	V	V	V	V	٧	V	N. C.
Timepoint	D1	D31	M6	M12	M18	M24	M30	M36	Notes
Study participant informed consent ¹	•								See Section 10.1.3 for details
Check with participant if he/she will appoint a caregiver and distribute caregiver information letter, when applicable	0	0	0	0	0	0	0	0	See Section 5.2.5 for details

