7. DISCONTINUATION OF STUDY INTERVENTION AND PARTICIPANT DISCONTINUATION/WITHDRAWAL

7.1. Discontinuation of study intervention

'Discontinuation' of study intervention means any participant who has not received all planned doses of vaccine. A participant who discontinued study intervention may, if deemed appropriate by the investigator, continue other study procedures (e.g., subsequent dose or revaccination, safety or immunogenicity) if planned in the study protocol.

The primary reason for premature discontinuation of the study intervention will be documented in the eCRF based on the following:

- AE requiring expedited reporting to GSK
- Unsolicited non-serious AE
- Solicited event
- Not willing to be vaccinated
- Other (specify).

Refer to Section 7.1.2 for contraindications to subsequent vaccination. Refer to the Glossary of terms for the definition of intervention.

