7.1.2. Contraindications to subsequent vaccine administration (Amended: 01 April 2022)

Participants in the RSV_annual *and RSV_flexible revaccination* groups must be evaluated to confirm they are eligible for subsequent vaccination before administering each additional study vaccine dose.

Participants who meet any of the criteria listed below or criteria listed in Sections 5.2.1 and 5.2.2 should not receive additional vaccinations. However, these participants should be encouraged to continue other study procedures at the discretion of the investigator (Section 10.3.8.2). The relevant criteria for discontinuing vaccination must be recorded in the eCRF.

- Participants who experience any SAE judged to be possibly or probably related to study vaccine or non-study vaccines, including hypersensitivity reactions.
- Participants who develop any new condition which, in the opinion of the investigator, may pose additional risk to the participant if he/she continues to participate in the study.
- Anaphylaxis following the administration of vaccine.
- Any condition that in the judgment of the investigator would make intramuscular injection unsafe.
- Occurrence of a new pIMD or the exacerbation of an existing pIMD that, in the opinion of the investigator, exposes the participant to unacceptable risk from subsequent vaccination. In such cases, the investigator should use his/her clinical judgment prior to administering the next dose of the vaccine. Refer to Section 10.3.5 for the definition of pIMDs.

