7.2. Participant discontinuation/withdrawal from the study

A participant is considered a 'withdrawal' from the study when no study procedure has occurred, no follow-up has been performed and no further information has been collected for this participant from the date of withdrawal/last contact.

From an analysis perspective, a 'withdrawal' from the study refers to any participant who did not return for the concluding visit foreseen in the protocol.

212496 (RSV OA=ADJ-004) Protocol Amendment 1 Final

Investigators will attempt to contact those participants who do not return for scheduled visits or follow-up.

All data and samples collected until the date of withdrawal/last contact of the participant will be used for the analysis.

The primary reason for study withdrawal will be documented in the eCRF based on the list below:

- AEs requiring expedited reporting to GSK (please refer to Section 10.3.10.1 for details)
- Unsolicited non-serious AE
- Solicited event
- Withdrawal by participant, not due to an AE*
- Migrated/moved from the study area
- Lost to follow-up
- Sponsor study termination
- Other (specify)

*If a participant is withdrawn from the study because he/she has withdrawn consent and provided the reason for its withdrawal, the investigator must document this reason in the eCRF.

Participants who are withdrawn from the study because of SAEs/AEs must be clearly distinguished from participants who are withdrawn for other reasons. Investigators will follow participants who are withdrawn from the study as result of an SAE/AE until the event is resolved (see Section 10.3.8.2).

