10.3.8.2.2. Follow-up after the participant is discharged from the study

The investigator will provide any new or updated relevant information on previously reported SAE/pIMD to GSK using a paper/electronic Expedited Adverse Events Report as applicable. The investigator is obliged to perform or arrange for the conduct of supplemental clinical examinations/tests and/or evaluations to elucidate the nature and/or causality of the AE or SAE as fully as possible.

10.3.8.3. Updating of SAE and pIMD information after removal of write access to the participant's eCRF

When additional SAE or pIMD information is received after removal of write access to the participant's eCRF, new or updated information should be recorded on the appropriate paper report, with all changes signed and dated by the investigator. The updated report should be faxed to the Study Contact for Reporting SAEs (refer to the Section 8.3.3.1 or to GSK Clinical Safety and Pharmacovigilance department within the defined reporting timeframes specified in the Table 15.

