5. STATISTICAL ANALYSES

Standard data derivation rules and stat methods are described in Section 10.1 while the study specific data derivation rules and stat methods are described in Section 9.

For the sake of analysis, data up to Month 12 will be analyzed by group (RSV_annual, RSV_flexible revaccination and RSV_1dose), and also the 3 groups will be pooled. For Month 13, Month 18 and Month 24, the analyses will be tabulated for RSV_annual group versus the pooled RSV_flexible revaccination and RSV_1dose groups. From Month 25 up to study end, the analyses will be performed by group

If more than 5% of participants in the RSV_annual and RSV_flexible revaccination groups receive different number of doses, an analysis by subgroup according to the number of dose(s) administered might be performed. The goal of this analysis is to describe the characteristics of participants in the RSV_annual and RSV_flexible revaccination groups who ultimately receive different numbers of revaccination doses in order to rule out the possibility of systematic differences between these subgroups.

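### SAP 5.4.6 reruns safety on participants who attended every visit, so at end of study its rows for deaths and AE-related study withdrawals are empty by design, and the set does not match its own trigger

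*SAP*

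**What the plan says.** SAP 5.4.4 runs the safety analysis on the ES. Its items include fatal SAEs from Day 1 to study end, and AEs/SAEs leading to discontinuation of the study or of the intervention.

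SAP 5.4.6 adds a conditional repeat. The trigger is that more than 10% of participants either miss the revaccination dose or have no safety data after it. Then "the safety analysis described in section 5.4.4 will also be conducted on participants with full follow-up (attending all study visits"). Full follow-up is not defined in any other way, and death is not excepted. The section gives its goal in general terms: to see how far results change under different scenarios. The only scenarios it names are the two in its trigger.

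Four other places bear on this:

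- Protocol 7.2: for analysis, a withdrawal "refers to any participant who did not return for the concluding visit foreseen in the protocol".
- Protocol 7.1, on missed doses: "A participant who discontinued study intervention may, if deemed appropriate by the investigator, continue other study procedures". Protocol 7.1.2, on contraindications: "these participants should be encouraged to continue other study procedures at the discretion of the investigator".
- Protocol 1.3, footnotes to the activity tables: any SAE or pIMD is recorded in RSV_annual "from Day 1 to Month 6, from Month 12 to Month 18, and from Month 24 to Month 30", and in RSV_flexible revaccination "from Day 1 to Month 6 and from Month 24 to Month 30".
- SAP 5: if more than 5% receive a different number of doses, "an analysis by subgroup according to the number of dose(s) administered might be performed".

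**The concern.** A sensitivity analysis for missed revaccination should vary who received the dose, or who has data after it. This one varies attendance over three years. Attendance is itself an outcome of death and of AEs that make people leave, so selecting on it removes exactly those events.

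The risk is one of reading. If the trigger fires, the repeat is mandatory, and it would place a fatal-SAE row of zero, with an exact confidence interval, beside the ES row. A reader could take the difference as a finding about follow-up when it follows from how the set is defined.

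**Working it through.** The plan gives no figure for the size of this set, so there is none to reproduce. The check is on definitions and on the visit schedule.

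**Step 1. Who can be in the set at end of study.** Tables 1 to 3 in Protocol 1.3 place study conclusion at Month 36, so Month 36 is the concluding visit. Let F be those who attended all visits and W the withdrawals under Protocol 7.2. Membership of F requires attendance at Month 36; membership of W requires non-attendance there. Hence F and W share no participant. Anyone who died before the Month 36 visit is also outside F.

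**Step 2. Effect on the items of SAP 5.4.4.**

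| Item | ES | Full-attendance set, end of study |
|---|---|---|
| Fatal SAE, death before the Month 36 visit | counted | 0 by construction |
| Fatal SAE, death after the Month 36 visit | can be counted if reported | can be counted if reported |
| AE/SAE leading to study withdrawal | counted | 0 by construction |
| AE/SAE leading only to stopping vaccination | counted | can remain |
| Other events | counted | counted for full attenders only; direction of change unknown |

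The second row exists because reporting continues after discharge (Protocol 10.3.8.2.2): "The investigator will provide any new or updated relevant information on previously reported SAE/pIMD to GSK". The fourth exists because SAP 5.4.4 puts study and intervention discontinuation in one item, and people who stop vaccination may keep attending.

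**Step 3. Trigger against set.**

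| Participant | Meets the trigger condition? | In the set? |
|---|---|---|
| Misses the dose, attends every visit | yes | yes |
| Revaccinated at Month 24, seen at Months 25 and 30, missed Month 6 | no | no |
| Revaccinated, has safety data after the dose, then dies before Month 36 | no | no |
| RSV_1dose, missed one visit | no revaccination to miss | no |

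Every row goes the wrong way for an analysis meant to isolate missed doses or missing post-dose data.

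**Step 4. How many unrelated visits can remove a recipient.** Scheduled visits number 10 in RSV_annual, 9 in RSV_flexible revaccination and 8 in RSV_1dose. For the Month 24 dose, the visits that carry the dose and its six-month window are Months 24, 25 and 30. Day 1 is attended by everyone dosed.

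- RSV_annual: 10 − 3 − 1 = 6 other visits (Day 31, Months 6, 12, 13, 18 and 36).
- RSV_flexible revaccination: 9 − 3 − 1 = 5 (the same without Month 13).

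Missing any one of these removes a recipient from that dose's tables. Month 36 does bear on the items collected to study end (fatal and related events), but not on the six-month tables for all SAEs and pIMDs.

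**Step 5. What cannot be calculated.** The documents give no attendance, withdrawal or death rate. The base of the 10% is not stated either: it could be 165 of 1650, 132 of the 1320 planned for revaccination (990 + 330), 99 of 990, or 33 of 330.

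**The case against.** A repeat on completers beside the full analysis is a familiar robustness check, and one attendance rule for all groups is simple. SAP 5.4.6 never says that its goal is confined to missed revaccination; that is inferred from the trigger. This stands: one cannot say that the section fails its stated goal, only that its set does not fit the scenarios it names.

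Part of the problem is handled elsewhere. Solicited events are analysed only in participants with documented diary data (SAP 5.1.3). Events are attributed to the latest dose (SAP 10.1.1). Diary compliance, doses by visit and withdrawals by reason are all tabulated. This also stands, but it does not change who enters the repeat. The analysis by number of doses in SAP 5 is optional and aims at participant characteristics, so it is no substitute.

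Three stronger readings are tempting and unsupported:

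- *Deaths or withdrawals disappear from the trial's safety results.* They do not. The ES analysis is primary, fatal SAEs are tabulated there and all SAEs are listed.
- *The set shrinks by a known amount, or hides a known number of deaths.* Any such figure needs assumed rates. The 20% a year in Protocol 9.2 is non-evaluability in the sample-size section, not study withdrawal. About 645 RSV_annual participants may have a contact in place of a visit at Months 6, 18, 30 and 36, and SAP 5.4.6 does not say whether that counts as attending. An assumed attendance may not even fire the trigger: at 95% per visit, taken as independent, the share of RSV_annual missing Month 12 or Month 24 is 1 − 0.95² = 9.75%, below 10%.
- *The repeat understates all event rates.* For events other than deaths and AE-related withdrawals, the direction is unclear.

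**Conclusion.** The point holds by definition. At end of study, the repeat must show zero AEs/SAEs leading to study withdrawal, and zero fatal SAEs apart from a death after the Month 36 visit. The mismatch with the trigger also holds, in both directions and for RSV_1dose.

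This rests on reading full follow-up as SAP 5.4.6 words it and on Protocol 7.2. It is limited to the end-of-study analysis, because at earlier analyses all study visits could be read as visits to date.

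The consequence is modest: a conditional, misleading set of tables in a study whose analyses are all descriptive. No event is lost and no decision rule is affected. It should be corrected because, once triggered, the repeat is mandatory and the correction is cheap.

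**What to change.** Replace the full-attendance set in SAP 5.4.6. For RSV_annual (Month 12 and Month 24 doses) and RSV_flexible revaccination (Month 24 dose), repeat the post-revaccination tables of 5.4.4 on all participants who received the dose in question, whatever their later attendance. Beside each table, report the number of recipients with no safety contact after that dose. A reported event must not by itself decide who enters: a rule of that kind admits people because they had an event, drops event-free people without contact, and so raises the rates.

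If a full-attendance table is kept, omit fatal SAEs and AEs/SAEs leading to study withdrawal from it and refer to the ES tables.

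The cost is a change of SAP wording and minor programming, with no new data. The denominator is smaller than the ES. Recipients with no later information still count as event-free for unsolicited AEs, SAEs and pIMDs under SAP 5.1.3; the reported count makes their number visible but does not remove the problem.
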